3.3 Recruitment

A total of 20 patients that are post kidney transplant, will undergo intervention until 3 months post-transplant. Informed consent will be obtained prior to start of study. The final visit will be at 3 months. Patients will be discharged to their local endocrinologist or primary care physician at this 3-month mark. Data will continue to be gathered for 3 more months after exit from intervention.

Enrollment will be within the first 2 weeks of hospital discharge.

Screening of patients will be done through the inpatient endocrinology consult list (seen in various floors in the main campus hospital), or the endocrine kidney transplant clinic list (patients seen at Q8). Endocrine providers (physicians, nurse practitioners, pharmacists) who take care of qualifying patients will inform patients of this study at their visits again only mentioning a research study involving CGMs and kidney transplant patients. The endocrine providers will notify the study staff if the patient has questions or would like to learn more. The study staff will follow-up with the patients, provide and thoroughly review the consent. The patients will be given time to review the consent ask questions prior to making a decision to participate. The consenting process will take place in a private exam room if outpatient, or in the hospital room if still admitted to the hospital. The process will be documented in EPIC.

Visits are standard of care (SOC) at the Kidney Transplant Clinic or at the Endocrinology clinic and will be virtual or in-person or telephone encounter (see table). Visits are twice a week for the first 3 weeks post discharge. Following this, visits will be every two weeks until the end of the steroid taper(final steroid dose), usually 7.5mg daily by 56 days after transplant (see table below). This is part of SOC.

Standard prednisone taper	
Post op day	Prednisone dose
2	60 mg twice a day
3	50 mg twice a day
4	40 mg twice a day

5	30 mg twice a day
6	30 mg AM and 15 mg PM
7-13	30 mg in AM
14-27	20 mg in AM
28-41	15 mg in AM
42-55	10 mg in AM
56 and beyond	7.5 mg in AM

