At Enrollment, insertion of Freestyle Libre 2 (or later version) sensor will be placed on upper arm. An account will also be set up on Libreview.com. This is part of SOC with diabetic patients who use CGMs. The patient will be asked to sign up on the product's platform (in this case for Freestyle Libre Abbott products, Libreview.com). We will be collecting data from the CGM ambulatory glucose profile (AGP) report or from phone/reader if we are unable to link to the patient's portal for certain visits. An insulin dosing protocol would be set up per patient. The patients would have already been seen by the inpatient endocrine team during the admission for their kidney transplant and would have been discharged on multiple daily insulin injection (MDII). This is part of the early recovery after surgery (ERAS) pathway that we have developed with the kidney transplant team. When patient is outpatient, we address dosing in order of priority by reducing or increasing the corresponding insulin by 10-100%. The range is wide to account for some doses that might be small (e.g. 2 units of rapid-acting insulin, for prednisone dose reduction, and for a change in appetite). We also make allowance for changing to non-insulin medications, as shown in the table.

Acceptable percentage of time that glucose levels are at a certain range, and insulin adjustment		
Glucose e and percentage of time it is acceptable for glucose levels to be in these ranges		Insulin adjustment by 10-100% (the range is wide to account for some doses that might be small, such as 2 units of rapid-acting insulin, for prednisone dose reduction, and for a change in appetite)
Time in very high range (>250mg/dL)	5% or less	Increasing the corresponding insulin if above 5%

Time in high (181-250 mg/dL) plus very high range	25% or less	Increasing the corresponding insulin if above 25%
Time In Range		
In range (70-180 mg/dL)	70% or greater	Continue to monitor but decrease if prednisone dose is decreasing
Time Below Range		
Time in low range (54-69 mg/dL) plus very low range	4% or less	Reducing the corresponding insulin if above 4% with option to reduce even if 4% or less (because we want to avoid further hypoglycemia)
Time in very low range (<54 mg/dL)	1% or less	Reducing the corresponding insulin if above 1% with option to reduce even if 1% or less (because we want to avoid further hypoglycemia)
Other insulin protocols		

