3.4 Statistical Methods

The goal of the present study is not hypothesis testing, but rather estimation. With 20 patients, and assuming that the standard deviation in the time in range will be no more than 20%, and time in range levels will be moderately correlated over time ($r = 0.5$), estimated changes in time in range will be estimated to within $\pm 9.4\%$. Additionally, there will be at least 80% power to detect mean changes of at least 13.3% in time in range over time within patients. This sample size will allow us to generally estimate precision of the prevalence of binary events such as readmission and delay of graft function to within $\pm 20\%$ provided that the event rate is less than 30%.

Patient characteristics will be summarized overall and by group using means and standard deviations for continuous measures and frequencies and percentages for categorical factors. Medication adjustment as well as binary events such as readmission, rejection and delayed graft function rates will be estimated at each time point and compared over time using McNemar tests or generalized mixed effect models. To evaluate continuous measures such as HbA1c and AGP metrics over time, paired t-tests or linear mixed models will be used. In these models, time will be the main predictor. Estimated HbA1c and glucometrics levels at each time with 95% confidence limits will be estimated from the model. Linear mixed models are valid under the assumption of missing at random. This will be evaluated graphically and, if necessary, sensitivity analyses will be performed to evaluate the potential effects of the missing data over time. If glucometric time measures are close to the extremes of the distribution (i.e. near 0 or 1), then an alternate approach using beta regression to estimate the levels and changes may be performed. Time to readmission and rejection will be estimated using Kaplan-Meier analysis. If interim analyses result in a change to the insulin dosing protocol, results will be presented overall, and then separately for the first 10 and last 10 patients. Stratification of results may also be performed based on the timing of enrollment relative to the transplant. Analysis will be performed using SAS software (version 9.4; Cary, NC) or R software (version 4.1; Vienna, Austria). Given that this is a pilot study, we will perform all tests using a 0.05 significance level, and focus on estimation to allow for future research, if warranted.

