4.3 Adverse Events and Data Monitoring Committee (DMC)

There will not be a data monitoring committee for this pilot project. Any AE or SAE will be reported to the PI, Sponsor and IRB in a timely manner once they have been disclosed to study personnel.

Unanticipated non-serious adverse events assessed by the PI as being either caused by, or related to, the study procedures, will be reported using the Adverse Event Report form.

The following adverse events are anticipated as a result of the blood collection required per the study procedures: pain, bruising, bleeding or infection at the site where the blood was collected from the subject. Fainting may also occur as a result of blood collection. Because these events are anticipated, they do NOT need to be reported using the Adverse Event Report form as long as they are not assessed as serious. If assessed as serious, then they need to be reported.

There may be some risks from wearing the Continuous Glucose Monitor (CGM)

- Skin irritation at the insertion site which may include redness and rash
- Infection at the insertion site (redness, soreness, warm or hot skin, drainage noted)
- Discomfort
- The sensor may fall off accidentally and need to be reinserted
- Exposing the sensor to MRI, CT scan, diathermy (electrically induced heat or the use of high frequency electromagnetic current as used in physical therapy or surgery), or x-ray may cause damage and incorrect readings. Patients will be asked to remove the sensor for these procedures.
- The sensor should not be submerged more than 3 feet (1 meter) or kept underwater longer than 30 minutes at a time.

Interim analysis of glucometrics:

Even though there is no DMC, we would like to see if our insulin dosing parameters are related to severe hyperglycemia and severe hypoglycemia. As such, we will do interim analysis after 10 patients. If among the first 10 patients, at least 4 patients report Time in Very High Range > 10% of the time, or Time in Very Low Range >5% of the time, then the insulin dosing protocol will be reviewed and modified.

5. DATA HANDLING AND RECORD KEEPING:

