A file database will be created for data collection accessible only by authorized study personnel. Information will be entered into the database as it is collected and patients finish the study. Each patient will be assigned a study number consecutively as they are enrolled. Only the study number will be used to identify all study-related documents such as case report forms. A master list of study numbers linked to patient identifiers will be maintained by the study coordinator in a secured location. Study data will be collected and managed using REDCap (Research Electronic Data Capture); this will include patient identification number, medical record number, age, gender, and ethnicity.

If a subject withdraws from the trial or is lost to follow-up, then the subject's data which has already been collected will be retained by the investigator, entered into the database and used for the study reporting.

6. ETHICS:

Protocol Version 2, Dated 6-24-2024

The study will be conducted in compliance with ICH GCP and applicable regulatory requirements, and in accordance with the Declaration of Helsinki.

Voluntary signed informed consent will be obtained from each study subject prior to initiating any research interventions. Informed consent will be documented in the subject's medical record.

This study is subject to the review and approval of the Cleveland Clinic Institutional Review Board prior to initiating any study activities.

7. PUBLICATION PLAN:

Upon study completion, the data generated will be submitted in abstract form to an endocrine-, diabetes-, or kidney transplant-related meeting, and subsequently submitted to a journal for consideration for publication.

8. CITATIONS:

Burrows NR et al. Reported Cases of End-Stage Kidney Disease — United States, 2000–2019. MMWR Recomm Reports. 2022;71(11):412-415

Hart A et al. OPTN/SRTR 2019 Annual Data Report. Am J Transplant 2021;21(2):21-137

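### If the interim look changes the insulin dosing protocol, Section 3.4 splits results by enrollment order rather than by version received, and nothing in the protocol makes the two coincide

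*Protocol*

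**What the plan says.** Section 3.4 (Statistical Methods) ties an extra display to one event, a change of the insulin dosing protocol after an interim analysis. In that case "results will be presented overall, and then separately for the first 10 and last 10 patients".

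The interim look is described at the end of Section 4.3: "we will do interim analysis after 10 patients". Its trigger begins "If among the first 10 patients, at least 4 patients report Time in Very High Range > 10% of the time", with a second threshold for very low glucose. If it is met, the dosing protocol is reviewed and changed.

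Other sections bear on how order relates to version:

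- Section 5: "Each patient will be assigned a study number consecutively as they are enrolled". Order is therefore order of enrollment.
- Section 3.3: the 20 patients "will undergo intervention until 3 months post-transplant", so one patient's participation can overlap with that of many others.
- Section 3.3: "At Enrollment, insertion of Freestyle Libre 2 (or later version) sensor will be placed on upper arm". CGM data for a patient start only then.
- Section 3.3: "An insulin dosing protocol would be set up per patient".

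Section 3.4 also sets the context: "The goal of the present study is not hypothesis testing, but rather estimation".

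**The concern.** Because the split is made only when the dosing protocol changes, its purpose must be to separate results before and after the change. Position in the enrollment sequence is a proxy for that, and the protocol does not secure the proxy. It does not say whether the look follows the tenth enrollment or the tenth completion, whether enrollment waits for the decision, or whether a change reaches patients already under treatment.

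If the proxy fails, one or both halves contain patients treated wholly or partly under the other version. The only old-versus-new display that the protocol specifies could then understate a real difference, in a study meant to inform later research.

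**Working it through.** **The plan's own figure.** With SD 20 and r = 0.5, the SD of a change is 20 × √(2 × (1 − 0.5)) = 20. The 95% half-width with n = 20 is t(0.975, 19) × 20/√20 = 9.36, which agrees with the stated ±9.4%. This point does not touch it.

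**When order equals version.** Two conditions are needed together:

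1. nobody enrolls as patient 11 or later before the change takes effect; and
2. either the first ten have completed the intervention, or the change covers new patients only.

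The look needs CGM percentages from the first ten, and the tenth sensor is placed at the tenth enrollment, so the look comes some time after that enrollment. Condition 1 therefore needs a pause or a gap in accrual. Setting up dosing per patient does not say that a patient's version is fixed at entry, so it does not secure condition 2.

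**How many patients could be misplaced.** Accrual is not stated. Assumptions: Poisson accrual at r = 1, 2 or 3 per month (30.44 days); enrollment uniform on days 3 to 17 after transplant (3-day stay from Section 1, then 0 to 14 days from Section 3.3); intervention ends on day 91. The mean time in the intervention is 91 − 10 = 81 days. Results come from 100,000 simulated trials per rate, with a closed form as a cross-check.

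| Scenario | Quantity | r = 1 | r = 2 | r = 3 |
|---|---|---|---|---|
| A: look after 10 completers, no pause | mean number of last ten who start on the original version | 2.7 | 5.3 | 7.6 |
| A | chance that none does | 7% | 0.5% | <0.1% |
| B: look 14 days after 10th enrollment, change for everyone | mean number of first ten who receive some of the modified version | 3.2 | 5.4 | 7.3 |
| C: look 14 days after 10th enrollment, new patients only, no pause | mean number of last ten on the original version | 0.46 | 0.92 | 1.38 |
| C | chance of none | 63% | 40% | 25% |
| D: both conditions met | number misplaced | 0 | 0 | 0 |

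Cross-checks:

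- A: r × 81/30.44 = 2.66, 5.32, 7.98. The last exceeds the simulated value because the count is capped at 10.
- B: 1 + r × (81 − 14)/30.44 = 3.20, 5.40, 7.60. The cap of 9 on earlier patients lowers the last.
- C: mean r × 14/30.44; chance of none exp(−r × 14/30.44) = 0.63, 0.40, 0.25.

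**How often the split would be made.** If each patient crosses either threshold with an assumed probability p, the chance that at least 4 of 10 do so (binomial) is 1%, 12%, 35% or 62% for p = 0.1, 0.2, 0.3 or 0.4.

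**Precision of the display.** For two groups of 10 at SD 20, the 95% half-width of a difference is t(0.975, 18) × 20 × √(1/10 + 1/10) = 2.101 × 8.944 = ±18.8 points.

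**The case against.** The strongest reply is that nothing in the protocol contradicts the split. Sections 3.4 and 4.3 can be read together as one plan in which patients 1 to 10 inform the review and patients 11 to 20 follow it, with operational detail left to a later document. That reading is possible. But it needs a pause or a near-instant decision, plus completion of the first ten or a change limited to new patients, and none of this is written. Nor is this only missing detail. The protocol itself fixes the grouping, and an analysis plan that followed it would inherit the problem.

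Several parts of the reply stand:

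- The counts above rest on assumed accrual, entry times and look date.
- Even a clean split into halves of 10 is imprecise.
- Medication, dose and CGM data are collected at the visits, so a display by version could be built afterwards if the date of the change is known. It would then be ad hoc rather than planned.
- Order-based halves are unambiguous and fixed in advance, which grouping by version is not.

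A reader might also infer that a look after ten completers must leave original-version patients among the last ten. It does so only if enrollment is not paused and someone enrolls in the interval. At 1 per month the chance that nobody does is 7% even without a pause.

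**Conclusion.** The point holds as a possible mismatch, not a certain one. The stated rule groups by order, its purpose calls for grouping by version, and the protocol does not make them agree. The number misplaced ranges from 0 to about 7 or 8 of 10 at an assumed 1 to 3 enrollments per month.

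It is minor, an optional to low-priority improvement. It arises only if the trigger leads to a change. The split is descriptive in a study aimed at estimation, the overall results are presented regardless, and no stated figure is wrong.

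A reader might go further and conclude that the before/after difference is biased by a calculable amount. The documents do not support that. The amount depends on accrual, the timing of the look, whom a change covers and how any effect of version varies over the steroid taper, and the protocol fixes none of these.

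**What to change.** In Section 3.4, replace the order-based split with groups by insulin-protocol version received: original only, modified only, and both, with the last listed descriptively. Record the date a change takes effect and the version or versions each patient received. The order-based display may be kept as a supplement. It would help if Section 4.3 also said whether the look follows ten enrollments or ten completions, and to whom a change applies. That choice is the sponsor's, and no view is taken here on the dosing content.

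The cost in text and data is small: a date, a version field and a few sentences. The statistical cost is groups that may be unequal and smaller than 10. Under scenario B at 2 per month, the means imply 10 − 5.37 ≈ 5 original only, 5.37 + 0.92 ≈ 6 both, and 10 − 0.92 ≈ 9 modified only. Original only versus modified only then has a half-width of t(0.975, 12) × 20 × √(1/5 + 1/9) = 2.179 × 11.16 ≈ ±24 points, against ±18.8 for 10 versus 10. The comparison is less precise, but each group is what its label says.

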4. STUDY POPULATION

This is a non-randomized perspective single arm study with a planned enrollment of 20 patients.

4.1 Inclusion Criteria

1. Sex: men and women
2. Ethnicity: all ethnic groups
3. Age: ≥ 18
4. Known type 2 diabetes before kidney transplant
5. Kidney transplant alone
6. On multiple daily insulin injection
7. Standard prednisone taper
8. Smart phone – compatible with the LibreView App

4.2 Exclusion Criteria

1. Simultaneous pancreas-kidney transplant
2. Allergy to Freestyle Libre components including adhesive
3. Use of vitamin C at doses 500 mg or greater
4. Blood dyscrasias that prevent hemoglobin A1c interpretation
5. Lack of mobile app accessibility
6. Rapid prednisone taper

In the uncommon scenario, if a patient is started on a standard prednisone taper and converted to a rapid prednisone taper. The patient would remain in the study.

4.3 Adverse Events and Data Monitoring Committee (DMC)

There will not be a data monitoring committee for this pilot project. Any AE or SAE will be reported to the PI, Sponsor and IRB in a timely manner once they have been disclosed to study personnel.

Unanticipated non-serious adverse events assessed by the PI as being either caused by, or related to, the study procedures, will be reported using the Adverse Event Report form.

The following adverse events are anticipated as a result of the blood collection required per the study procedures: pain, bruising, bleeding or infection at the site where the blood was collected from the subject. Fainting may also occur as a result of blood collection. Because these events are anticipated, they do NOT need to be reported using the Adverse Event Report form as long as they are not assessed as serious. If assessed as serious, then they need to be reported.

There may be some risks from wearing the Continuous Glucose Monitor (CGM)

- Skin irritation at the insertion site which may include redness and rash
- Infection at the insertion site (redness, soreness, warm or hot skin, drainage noted)
- Discomfort
- The sensor may fall off accidentally and need to be reinserted
- Exposing the sensor to MRI, CT scan, diathermy (electrically induced heat or the use of high frequency electromagnetic current as used in physical therapy or surgery), or x-ray may cause damage and incorrect readings. Patients will be asked to remove the sensor for these procedures.
- The sensor should not be submerged more than 3 feet (1 meter) or kept underwater longer than 30 minutes at a time.

Interim analysis of glucometrics:

Even though there is no DMC, we would like to see if our insulin dosing parameters are related to severe hyperglycemia and severe hypoglycemia. As such, we will do interim analysis after 10 patients. If among the first 10 patients, at least 4 patients report Time in Very High Range > 10% of the time, or Time in Very Low Range >5% of the time, then the insulin dosing protocol will be reviewed and modified.

5. DATA HANDLING AND RECORD KEEPING:

A file database will be created for data collection accessible only by authorized study personnel. Information will be entered into the database as it is collected and patients finish the study. Each patient will be assigned a study number consecutively as they are enrolled. Only the study number will be used to identify all study-related documents such as case report forms. A master list of study numbers linked to patient identifiers will be maintained by the study coordinator in a secured location. Study data will be collected and managed using REDCap (Research Electronic Data Capture); this will include patient identification number, medical record number, age, gender, and ethnicity.

If a subject withdraws from the trial or is lost to follow-up, then the subject's data which has already been collected will be retained by the investigator, entered into the database and used for the study reporting.

6. ETHICS:

Protocol Version 2, Dated 6-24-2024

The study will be conducted in compliance with ICH GCP and applicable regulatory requirements, and in accordance with the Declaration of Helsinki.

Voluntary signed informed consent will be obtained from each study subject prior to initiating any research interventions. Informed consent will be documented in the subject's medical record.

This study is subject to the review and approval of the Cleveland Clinic Institutional Review Board prior to initiating any study activities.

7. PUBLICATION PLAN:

Upon study completion, the data generated will be submitted in abstract form to an endocrine-, diabetes-, or kidney transplant-related meeting, and subsequently submitted to a journal for consideration for publication.

8. CITATIONS:

Burrows NR et al. Reported Cases of End-Stage Kidney Disease — United States, 2000–2019. MMWR Recomm Reports. 2022;71(11):412-415

Hart A et al. OPTN/SRTR 2019 Annual Data Report. Am J Transplant 2021;21(2):21-137

